### **Sample Size Estimates and Power Calculations**

The database for FY 2010/11 shows that 386 clinics fit the criteria with 89 sites available for arms 1-2 and 297 available for the comparison group. The mean number of female clients aged 21-29 years seen at the eligible clinics was 560 and the mean number of cytology specimens, colposcopic examinations and LEEP/cryoprocures for this age group was 297, 40, and 4, respectively. In 2012, the mean cytology interval was 19 months. Very few clinics had an interval >30 months. There were no differences for any of the above variables between those

sites eligible for intervention and those for comparison. These numbers have not changed significantly in the past 2 years and will be updated for the baseline assessment.

After enrolling 7 sites into each arm, we estimate that we would have approximately 2800-3500 women aged 21-29 years in each arm. For each arm, baseline cytology rate in this age group would be approximately 50%, rate of colposcopy procedures for those who had cytology would be 13%, and rate of LEEP/cryotherapy procedures for those referred to colposcopy would be 10%.

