**b) To increase average length of cervical cytology testing among women under 30 years of age**

**Pre:** cervical cytology test interval among women who received two CC tests from same provider (analysis limited to providers who have been in program at least 36 months)

**Post:** cervical cytology test interval among women who received their second CC test 3-15 months after the intervention started.

**c)** To decrease the number of LEEP and cryotherapy procedures in women under 30 years of age with abnormal cytology.

**Pre:** Rate of women 21-29 years of age who receive LEEP or cryotherapy over total number of women 21-29 years of age in quarter before intervention started.

**Post:** Rate of women 21-29 years of age who receive colposcopy or LEEP or cryotherapy over total number of women 21-29 years of age in 3-6, 9-12, and 15-18 months after intervention started.

**d)** To decrease the number of colposcopy procedures in women 21-24 years of age with abnormal cytology.

**Pre:** Rate of women 21-24 years of age who receive colposcopy over total number of women 21-24 years in quarter before intervention started.

**Post:** Rate of women 21-24 years who receive colposcopy over total number of women 21-24 years of age in 3-6, 9-12, and 15-18 months after intervention started.

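### Endpoint (c) counts LEEP or cryotherapy before the intervention but adds colposcopy afterwards, which builds in a roughly ten-fold artificial rise and swamps the treatment signal

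*Combined protocol and SAP*

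**What the plan says.** Under Data Analyses, item c) gives its aim as "To decrease the number of LEEP and cryotherapy procedures in women under 30 years of age with abnormal cytology". The pre-intervention measure fits that aim: "Rate of women 21-29 years of age who receive LEEP or cryotherapy over total number of women 21-29 years of age in quarter before intervention". The post-intervention measure, taken in three later windows (months 3-6, 9-12 and 15-18), is "Rate of women 21-29 years of age who receive colposcopy or LEEP or cryotherapy over total number of women 21-29 years of age". Age band and denominator are the same in both lines; only the numerator differs.

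The paragraph after the outcome list says that the primary endpoint compares within-clinic changes between groups, and that the secondary endpoints follow a similar approach. The opening line of Data Analyses adds that outcomes are evaluated within arms as well as between them. Colposcopy has its own item, d), restricted to ages 21-24, with matching pre and post definitions. Nothing in the document explains or corrects the mismatch in c).

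**The concern.** A change score has meaning only if the same event is counted at both ends. Here the later count includes a diagnostic examination that the earlier count leaves out, and by the plan's own figures that examination is ten times as frequent as the treatments.

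Two things follow. Every within-arm change would show a large apparent increase in an outcome that the trial hopes to reduce. The between-arm contrast would be mainly a colposcopy contrast, partly repeating item d). A woman who has both a colposcopy and a LEEP in the same window counts once, so sparing her the LEEP would leave the post rate unchanged.

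Overtreatment with excisional procedures is one of the two harms that the Project Summary sets out to reduce, and item c) is the only analysis definition that covers it.

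**Working it through.** **Inputs, from Sample Size Estimates and Power Calculations.** "The mean number of female clients aged 21-29 years seen at the eligible clinics was 560". The mean counts of cytology specimens, colposcopies and "LEEP/cryoprocures for this age group was 297, 40, and 4, respectively". The planning rates are "baseline cytology rate in this age group would be approximately 50" per cent, 13% colposcopy among women with cytology, and "rate of LEEP/cryotherapy procedures for those referred to colposcopy would be 10" per cent.

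**Reproducing the plan's rates**
- Colposcopy among women with cytology: 40/297 = 13.5% (stated 13%).
- LEEP/cryotherapy among women referred to colposcopy: 4/40 = 10.0% (stated 10%).
- Cytology: 297/560 = 53% (stated as about 50%). This rate cancels from the post-to-pre ratio.

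The plan states that it made no power calculation for the LEEP outcome, so there is no such figure to reproduce.

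**Assumptions.** The document does not say how many treated women also have a colposcopy in the same window, so the overlap is taken over its full range, 0% to 100%. One colposcopy per woman examined is assumed first and then relaxed.

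**Endpoint (c) as written, with no true change**

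Post = colposcopy rate + treatment rate × (1 − overlap); Pre = treatment rate.

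| Source | Pre | Post, full overlap | Post, no overlap | Ratio | Change (points) |
|---|---|---|---|---|---|
| Clinic means | 4/560 = 0.71% | 40/560 = 7.14% | 44/560 = 7.86% | 10.0 to 11.0 | +6.4 to +7.1 |
| Planning rates | 0.50 × 0.13 × 0.10 = 0.65% | 0.50 × 0.13 = 6.50% | 6.50% + 0.65% = 7.15% | 10.0 to 11.0 | +5.9 to +6.5 |

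Colposcopy supplies between 40/44 = 91% (no overlap) and 100% (full overlap) of the post events.

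**Repeat examinations.** The published figures count examinations, whereas the endpoint counts women. At an assumed 1.5 examinations per woman, 40/1.5 = 26.7 women and the ratio is 6.7 to 7.7. At 2 per woman, 40/2 = 20 women and the ratio is 5.0 to 6.0.

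**Between-arm difference in change** (clinic means; comparison arm unchanged)

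| What happens in the intervention arm | Endpoint (c) as written | LEEP/cryotherapy in both periods |
|---|---|---|
| Nothing | 0 | 0 |
| Colposcopy falls 20%, treatment unchanged | −8/560 = −1.4 points | 0 |
| Treatment halves (4 to 2), colposcopy unchanged | 0 (full overlap) to −2/560 = −0.36 points (no overlap) | −0.36 points |

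The 20% is illustrative. It is the size of the drop in women eligible for colposcopy that the plan assumes in its own colposcopy power calculation. A chance difference of only 10% in colposcopy would move the numerator by 4 women, twice the most that halving treatment could move it.

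**After correction, with no true change:** 0.71% before and 0.71% after; change 0, ratio 1.0.

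**The case against.** The strongest reply is that this is a drafting slip. The aim of item c), its pre line and the separate LEEP outcome named in the power section all point to LEEP or cryotherapy alone, and a careful analyst would notice. That is probably right about intent. But the post line is the operative numerator for a claims extraction, and nothing elsewhere overrides it. A correction made after the data have been seen would look like a change of outcome.

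Second, the artificial rise occurs in every arm, so it cancels in the between-arm test if colposcopy moves equally everywhere. That is true, and the rise alone creates no false arm difference. The condition is not one to rely on, because reducing colposcopy is a stated objective of the interventions. The within-arm changes are wrong in any case.

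Three narrower points stand. Treatment drops out of the endpoint altogether only at full overlap; otherwise it is up to 4/44 = 9% of post events. The ten-fold figure uses yearly counts of examinations; it carries over to quarterly counts of women if both procedures scale alike, and falls to about 5- to 8-fold if women average 1.5 to 2 examinations within the window. And endpoint (c) is secondary and unpowered; the primary endpoint, cytology rate, is defined consistently and is unaffected.

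**Conclusion.** The concern holds: endpoint (c) is wrong as written. Followed literally, it shows a rise from 0.7% to between 7.1% and 7.9% in every arm with no change in practice, about 10- to 11-fold on the plan's own figures. The size assumes one colposcopy per woman and equal scaling of both procedures from year to quarter. With repeat examinations it could be nearer 5- to 8-fold, which would still make the within-arm change uninterpretable.

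The between-arm result can mislead in both directions. A fall in colposcopy alone could be reported as reduced treatment, and a real halving of treatment could be invisible or lost in ordinary variation in colposcopy. This must be fixed before analysis, because no other defined endpoint covers treatment.

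**What to change.** In item c), delete 'colposcopy or' from the post-intervention definition, so that both periods count women aged 21-29 with LEEP or cryotherapy over all women aged 21-29. Colposcopy stays in item d). The deletion loses no valid comparison, since the plan has no matching pre-intervention colposcopy measure for ages 21-29. If colposcopy at 21-29 is wanted, it should be a separate outcome with its own matching pre and post definitions.

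The edit is two words. It needs no new data, sites or sample size, and it should be dated before outcome data are examined.

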Parallel calculations for the secondary colposcopy outcome also are based on between-arm comparison of changes in three-month colposcopy rates from baseline levels, and assume that approximately 50% of women will receive cytology at baseline and follow-up in the control group, and that colposcopy rates will also remain unchanged at 13%. We also assume that the intervention-related reduction in cytology will result in approximately 20% fewer women eligible for colposcopy at follow-up. Based on similar assumptions about intracluster correlation and loss to follow-up, results indicate that with the planned total sample size of 9030, we will retain at least 80% power to detect an intervention-related reduction in colposcopy rate as small as 8% at the 5% (one-sided) significance level. Due to our conservative assumptions, we should have sufficient power to detect even smaller intervention-related effects in analyses adjusting for baseline characteristics.

We did not perform calculations for the testing interval length and LEEP outcomes because of the lack of preliminary data on their potential variability within and between clinics.

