### Data Analyses

Outcomes to be evaluated within and between intervention arms are based on the specific research aims:

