The primary outcome measure will compare the observed within-clinic changes in cervical cytology testing rates between intervention and comparison groups using a t-test accounting for clinic-level clustering. We will use the same approach to test differences between each of the APP and APP + PCA and the comparison groups. Tests will be adjusted for multiple comparisons. Secondary endpoints include examining the interval between tests for women who received two cervical cytology tests from the same provider and the decrease in the number (and percent) of women receiving colposcopy procedures and LEEP or cryotherapy procedures. These will be analyzed using a similar approach as adopted for the primary endpoint. Patient satisfaction surveys will be administered to all women evaluated and compared between interventions and the controls. Because most available data is on the clinic level, we will have limited opportunities to analyze patient-level data. However we will be able to conduct supplementary analyses to investigate the possible impacts of between-arm imbalances in clinic level characteristics such as racial/ethnic composition, age distribution, descriptors of lab procedures, additional app or educational materials that are not part of the assigned intervention, and cervical cancer screening educational activities. Prior to starting the intervention and during the study, administrators and physicians at each clinic site will be asked about possible confounding variables at their clinic.

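### Outcome (c) counts LEEP or cryotherapy before the intervention but adds colposcopy afterwards, so about 90% of the Post numerator would be women who had colposcopy only

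*Combined protocol and SAP*

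**What the plan says.** All references are to the combined protocol and SAP.

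Under Analytic Methods, Data Analyses, outcome (c) has three parts:

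- Aim: "To decrease the number of LEEP and cryotherapy procedures in women under 30 years of age with abnormal cytology".
- Pre: the rate of women "who receive LEEP or cryotherapy over total number of women 21-29 years of age in quarter before intervention started".
- Post: the rate of women "who receive colposcopy or LEEP or cryotherapy over total number of women 21-29 years of age", in three windows after the start of the intervention.

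The denominator is the same in both periods; the numerator is not. Outcomes (a) and (d) in the same list use the same numerator before and after. Colposcopy has its own outcome, (d), limited to ages 21-24.

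The list is introduced with "Outcomes to be evaluated within and between intervention arms". The text after it names, as secondary endpoints, falls in the number and percentage of "women receiving colposcopy procedures and LEEP or cryotherapy procedures". These are to be analysed like the primary endpoint, which compares within-clinic changes between groups. The sample size section powers colposcopy separately and says of the other secondary outcomes: "We did not perform calculations for the testing interval length and LEEP outcomes".

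**The concern.** A change score means something only if the same quantity is measured at both times. Here the Pre rate measures treatment, while the Post rate measures any of colposcopy, LEEP or cryotherapy. Colposcopy is about ten times as common as treatment in these clinics, so it would dominate the Post rate.

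Three things are at stake:

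- **Within an arm**, the outcome would appear to worsen sharply even if nothing changed.
- **Between arms**, a difference in colposcopy could be read as a difference in treatment, and a real fall in treatment could be nearly invisible.
- **Good practice could be hidden.** The Screening and Management Guidelines section prefers colposcopic and cytological follow-up to treatment in young women. A woman moved from LEEP to colposcopic follow-up, which is what the intervention seeks, can still count in the Post numerator.

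Reducing overtreatment is a stated objective, and (c) is the outcome that measures it.

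**Working it through.** **Inputs** (Sample Size Estimates and Power Calculations). The mean number of women aged 21-29 per eligible clinic is 560, and "the mean number of cytology specimens, colposcopic examinations and LEEP/cryoprocures for this age group was 297, 40, and 4, respectively". Write C = 40 for colposcopies and L = 4 for treatments. One procedure of each kind per woman is assumed. Overlap between colposcopy and treatment in the same window is not given, so both extremes are shown.

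**The plan's own rates, reproduced.** 297/560 = 53.0% (stated as about 50%); 40/297 = 13.5% (stated 13%); 4/40 = 10.0% (stated 10%).

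**Make-up of Post (c).**

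- Full overlap (every treated woman also has a colposcopy): numerator C = 40; colposcopy-only share (C - L)/C = 36/40 = 90.0%. Post (c) is then exactly the colposcopy rate, and treatment cannot move it.
- No overlap: numerator C + L = 44; share C/(C + L) = 40/44 = 90.9%.

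**Change within an arm when practice does not change.**

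- Pre: 4/560 = 0.71%.
- Post: 40/560 = 7.14% to 44/560 = 7.86%.
- Rise: 40/4 = 10-fold to 44/4 = 11-fold, or +6.43 to +7.14 percentage points. With matching numerators the change is 0.

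The planned arm size and rates agree: 3010 x 0.50 x 0.13 = 195.65 colposcopies and 195.65 x 0.10 = 19.57 treatments. The ratios are 195.65/19.57 = 10 and 215.2/19.57 = 11.

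**Difference in change between arms** (one arm changes as described, the comparison arm does not):

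| Scenario | Post (c) as written, full / no overlap | Difference as written | Difference with (c) corrected |
|---|---|---|---|
| All treatment stops, colposcopy unchanged | 40 to 40 (0%) / 44 to 40 (-9.1%) | 0 to -4/560 = -0.71 points | -4/560 = -0.71 points |
| Colposcopy falls 20% (8 untreated women), treatment unchanged | 40 to 32 (-20%) / 44 to 36 (-18.2%) | -8/560 = -1.43 points | 0 |

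The 20% is borrowed as an illustration from the colposcopy power calculation, which assumes that the "intervention-related reduction in cytology will result in approximately 20% fewer women eligible for colposcopy at follow-up". In the second scenario the as-written outcome moves twice as far (8/4 = 2) as ending all treatment could move it, although treatment has not changed.

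**Incomplete cancellation.** Because Pre omits colposcopy, the change score cannot remove a clinic's baseline colposcopy level. A 10% baseline gap between arms is 4 of 40 women, as large as the whole treatment rate.

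**Sensitivity.**

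- Repeat colposcopies (an assumption; the plan gives no figure): at 1.25, 1.5 or 2 per woman the colposcopy-only share is 87.5-88.9%, 85.0-87.0% or 80.0-83.3%. At 2 per woman the artificial rise is 20/4 = 5-fold to 24/4 = 6-fold.
- Time scale: if the clinic means are annual and 560 stays the denominator, quarterly point values are a quarter of those above. The artificial rise becomes +1.6 to +1.8 points, 0.71 becomes 0.18 and 1.43 becomes 0.36. Ratios and shares do not change if both procedures scale alike.

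**The case against.** The strongest reply is that this is an obvious slip with little inferential effect. The aim, the Pre line and the separate mention of LEEP outcomes in the sample size section all show what was meant. An analyst would notice a tenfold rise in every group, comparison clinics included. The planned test compares changes between groups that share the definition, so most of the artificial rise drops out. All of this is fair. It limits the damage but does not correct the rule: no other section gives a numerator for (c), and after cancellation the remaining contrast is still mostly colposcopy.

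A second reply is that the 20% scenario is selective. The plan expresses treatment as 10% of women referred to colposcopy. Carried through that chain, a 20% fall in colposcopy takes treatment from 4 to 3.2. Corrected (c) then falls 20% (-0.8/560 = -0.14 points), and as-written (c) also falls 20% (40 to 32, or 44 to 35.2). Direction and relative size agree. This stands: the misleading result needs colposcopy to fall mainly among women who would not have been treated. That is plausible, because the intervention targets colposcopy for minimally abnormal cytology, but the plan does not assume it. The defect does not depend on this scenario.

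Third, the plan counts procedures in one place and women in the other, and the time scale of the clinic means is uncertain. The sensitivity figures cover both points, and colposcopy dominates throughout.

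Finally, the added words may be the remains of an intended colposcopy outcome for ages 21-29. The power calculation for colposcopy uses all 9030 women, while (d) covers only ages 21-24. That would call for a separate outcome line. It does not justify different numerators within (c).

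**Conclusion.** The concern holds. As written, outcome (c) measures different things before and after the intervention. On the plan's clinic means, 90-91% of the Post numerator would be colposcopy-only women, and the within-arm rate would rise 10- to 11-fold with no change in practice. This assumes one procedure of each kind per woman and baseline frequencies carrying forward; the share falls to 80-83% if women average two colposcopies each.

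Between arms the damage is smaller but real. Most of the artificial rise cancels, and the outcome then responds mainly to colposcopy. The primary outcome is untouched, and (c) is an unpowered secondary outcome. The point should be corrected before analysis, but it does not threaten the trial's main conclusion.

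**What to change.** In Data Analyses, outcome (c), delete *colposcopy or* from the Post definition, so that both periods count women aged 21-29 with LEEP or cryotherapy. Keep colposcopy in (d). If colposcopy at ages 21-29 is also of interest, as the power calculation on the full sample suggests, add it as a separate outcome with the same numerator in Pre and Post.

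The correction removes two words and needs no new data, visits or analyses. The optional extra line uses the same claims data.

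### The colposcopy aim, formula and power calculation use three different denominators, so the stated 80% power does not apply to the endpoint analysed, and less testing alone would lower that endpoint

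*Combined protocol and SAP*

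**What the plan says.** Three parts of the plan describe the colposcopy outcome, each with its own denominator.

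- **Aim** (Data Analyses, outcome (d)): "To decrease the number of colposcopy procedures in women 21-24 years of age with abnormal cytology".
- **Formula** (same place, pre-intervention): "Rate of women 21-24 years of age who receive colposcopy over total number of women 21-24 years in quarter before intervention started". The post-intervention formula has the same form, for months 3-6, 9-12 and 15-18.
- **Power** (Sample Size Estimates and Power Calculations): the baseline is introduced as "rate of colposcopy procedures for those who had cytology would be 13" per cent. The calculation assumes that about half of control women have cytology, that control colposcopy stays at 13%, and that the fall in cytology leaves about 20% fewer women eligible for colposcopy. It claims at least 80% power for a reduction as small as 8%, one-sided 5%, on the full sample of 9030 women aged 21-29.

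LEEP/cryotherapy shows the same pattern. The aim is "To decrease the number of LEEP and cryotherapy procedures in women under 30 years of age with abnormal cytology". The pre-intervention formula is "Rate of women 21-29 years of age who receive LEEP or cryotherapy over total number of women 21-29 years of age in quarter". The baseline uses yet another denominator: "rate of LEEP/cryotherapy procedures for those referred to colposcopy would be 10" per cent. The sample size section says that no power calculation was made for LEEP.

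The mean clinic saw 560 women aged 21-29, and the mean numbers of cytology specimens, colposcopies and LEEP/cryotherapy procedures "for this age group was 297, 40, and 4, respectively".

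**The concern.** A rate over all women is the product of two things: how many women are tested, and how often a tested woman goes on to colposcopy. The first is the primary outcome. The second is closer to what aim (d) names. Choice of Comparators lists longer screening intervals, fewer colposcopies after minimally abnormal results, and less treatment of lesions likely to regress as distinct targets. With the formulas as written, outcomes (c) and (d) cannot separate the last two from the first. No section plans a rate per woman tested or per woman with an abnormal result.

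The power statement has a related fault. It is built on a denominator that shrinks as testing falls, while the formula's denominator does not, and it uses a wider age band than the formula. A reader who relies on the 80% would be relying on a figure for a different quantity.

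**Working it through.** **1. The plan's own figure, on its own denominator.** Inputs: 7 clinics per arm, 430 women per clinic, intracluster correlation (ICC) 0.07, 13% against 5% (8% read as points), one-sided 5%. Women with cytology per clinic: 430 x 0.50 = 215 control, and 215 x 0.80 = 172 intervention.

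- Design effects: 1 + 214 x 0.07 = 15.98; 1 + 171 x 0.07 = 12.97.
- Variance: 0.13 x 0.87 x 15.98/(7 x 215) + 0.05 x 0.95 x 12.97/(7 x 172) = 0.00120 + 0.00051 = 0.00171; standard error 0.0414.
- 0.08/0.0414 = 1.93; 1.93 - 1.645 = 0.29; power about 61%.

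Pooled variance, a t reference with 12 df and 10% loss give 57-61%, so the stated 80% is not reproduced. Reaching it needs an ICC near 0.035-0.040, or a variance 40-47% smaller from pre/post pairing; the plan gives no such correlation. This shortfall is separate, and the denominator point does not depend on it.

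Read as a relative 8% (13% to 11.96%), the same method gives about 8% power.

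**2. Baseline on the formula's denominator.**

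- From the power assumptions: 0.50 x 0.13 = 6.5%.
- From the clinic means: 40/560 = 7.1%. (297/560 = 53% and 40/297 = 13.5% confirm where the plan's 50% and 13% come from.)

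These are fiscal-year figures for ages 21-29, and the 40 counts examinations, so the proportion of women is at most 7.1%. The formula is quarterly. Assume an even spread, so 40/4 = 10 colposcopies per quarter. If all 560 women count in every quarter, the rate is 10/560 = 1.8%. If each attends in one quarter only, it is 10/140 = 7.1%. The documents support that range, not a single value, and give no figure for ages 21-24.

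An 8-point fall exceeds every value in the range.

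**3. What could be detected on that denominator.** With 6.5%, all 430 women per clinic, ICC 0.07 and no gain from pairing:

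- Combining the plan's assumptions (cytology 50% to 40%, colposcopy per cytology 13% to 5%) gives 6.5% to 0.40 x 0.05 = 2.0%. Power is about 47% (normal) or 43% (t), one-sided.
- 80% power needs a fall of about 6.3 of the 6.5 points (normal). With the t reference even a fall to zero gives only 79%.

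**4. Effect of testing alone.** Colposcopy over all women = cytology rate x colposcopy per cytology. Hold the latter at 13%:

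| Cytology | Colposcopy / all women | LEEP or cryotherapy / all women (10% of colposcopies) |
|---|---|---|
| 50% | 6.5% | 0.65% |
| 40% (the plan's 20% fall) | 5.2% | 0.52% |
| 34% (the 16-point primary effect) | 4.4% | 0.44% |

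Conversely, colposcopy per tested woman could rise to 0.065/0.40 = 16% or 0.065/0.34 = 19% before the formula's rate stopped falling.

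The LEEP column assumes the same numerator before and after. As printed, the post-intervention formula in (c) is "Rate of women 21-29 years of age who receive colposcopy or LEEP or cryotherapy over total number of women 21-29 years of age", which adds colposcopy. That needs correcting in its own right: with no real change it would compare about 0.65% with about 6.5%.

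**The case against.** The strongest defence is that the all-women rate is a legitimate endpoint and that its dependence on testing is intended. Study Objectives seeks fewer colposcopies and excisional procedures without restricting this to abnormal results. The guideline background notes that annual screening produced twice the colposcopies of three-yearly screening. The paragraph defining the secondary endpoints speaks only of the number and percentage of women receiving the procedures. This stands: the rate measures procedure burden properly and should be kept.

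Three stronger readings are tempting, and the documents do not support them.

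- A reader might infer that the trial would announce better management on the strength of (d). No section says how (d) will be interpreted; the plan only leaves that reading open through the wording of the aim.
- A reader might take 1.8% as the quarterly baseline, or 32% (6.5% to 4.4%) as the expected mechanical fall. The first requires all the year's women to count in each quarter. The second uses the primary detectable difference rather than the 20% assumed for colposcopy. It is also close to an upper bound, because colposcopy is described as following persistent abnormality or as surveillance, so some in any window stem from earlier tests.
- A reader might extend the power criticism to LEEP/cryotherapy. No LEEP power was claimed, so there is none to contradict.

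It is also fair that a rate per woman with cytology is not a rate per woman with abnormal cytology, and that it conditions on something the intervention changes. It can support an interpretation but cannot carry one alone. Whether the claims hold cytology results is not stated.

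**Conclusion.** The point holds for colposcopy: aim, formula and power calculation rest on three denominators, and the power also uses a wider age band than the endpoint. On the only documented all-women baseline (6.5-7.1%; about 1.8-7.1% per quarter), an 8-point reduction is impossible, and the 80% claim does not apply to the endpoint analysed. This uses ages 21-29 as a stand-in for 21-24 and the plan's assumption of no change in controls. With 50% cytology, women aged 21-24 would need more than 16% colposcopy per cytology (0.08/0.50) for an 8-point fall to be arithmetically possible.

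If colposcopy tracks cytology in proportion, a 20% fall in testing alone takes the all-women rate from 6.5% to 5.2%. Outcomes (c) and (d) therefore cannot by themselves show a change in how abnormal results are managed. Only secondary outcomes are affected; the primary cytology rate is defined over all women and is untouched.

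**What to change.** 1. Keep the all-women rate as the secondary outcome for (c) and (d), and describe it as procedure burden, so that the stated aim matches the formula.
2. Co-report colposcopy and LEEP/cryotherapy per woman with cytology, or per woman with abnormal cytology if the claims hold results. Label this supportive, and state that it conditions on a post-intervention event and that colposcopies in a window may follow earlier tests.
3. State that a fall in the all-women rate alone will not be interpreted as better management of abnormal results.
4. Withdraw the 8%/80% statement. Replace it with the detectable difference computed on the all-women, three-month, age 21-24 baseline, saying whether it is in points or relative terms. No power claim is needed for LEEP/cryotherapy.
5. While editing (c), use the same numerator before and after.

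The per-cytology rates come from counts already extracted; the restated power needs one baseline tabulation for ages 21-24. The cost is a less favourable detectable difference and a supportive ratio that needs careful wording.
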